A Randomized Controlled Trial for Epidural Analgesia in the Morbidly Obese Parturient: Comparison of Dural Puncture Epidural with Standard Labor Epidural Techniques

NCT03074695

Document Date: May 16, 2018

Title: A Randomized Controlled Trial for Epidural Analgesia in the Morbidly Obese Parturient: Comparison of Dural Puncture Epidural with Standard Labor Epidural Techniques

Background and significance:

The incidence of morbid obesity in the United States is increasing, and in the last 30 years, the number of the super morbidly obese [body mass index (BMI) over 50 kg/m²] has risen 10-fold.¹ In obstetric patients, morbid obesity often complicates the placement of neuraxial labor analgesia due to difficulties in positioning patients for placement and identifying landmarks. Morbid obesity also significantly increases a woman's risk of requiring operative vaginal delivery or cesarean delivery after a trial of labor.² Further, there is a strong correlation with increasing BMI and risk of emergency cesarean section.³ A study by Hood *et. al* reports that in laboring women, 48% of morbid obese women (median BMI 52 kg/m²) require emergency cesarean while only 9% of the control group went on for emergency cesarean delivery.⁴

Neuraxial anesthesia is well-established as the preferred anesthetic technique for cesarean delivery due to the increased risks of administering general anesthesia to pregnant women. This is particularly relevant in the obese population since obesity increase the risk of difficult intubation. The Confidential Enquiry into Maternal Deaths in the United Kingdom cites obesity as a major risk factor in failed intubations, and Hawkins *et. al* report that aspiration of gastric contents during intubation is the leading cause of anesthesia-related death in the US obstetric population. ^{5,6} A labor epidural which can be satisfactorily extended to anesthetic conversion avoids the need for general anesthesia for cesarean section after trial of labor. Therefore, an early, established epidural (EPL) may prevent emergent administration of general anesthesia and greatly reduce the associated risks of serious complications.

Unfortunately, placement of an adequate neuraxial block can be challenging for the

anesthesiologist. Usual landmarks, such as spinal processes to indicate midline and iliac crests for vertebral level are often not visible or even palpable. Furthermore, adipose pockets in the subcutaneous layer result in false spaces with loss-of-resistance technique. One study has found a 42% EPL failure rate in the morbidly obese. Therefore, it should be a priority to establish regional anesthesia early in labor.

In modern practice, combined-spinal epidurals (CSE) have been used widely for labor analgesia. Benefits of the CSE include: more rapid onset, decreased motor block, and uniform sensory blockade. In practice, however, some clinicians avoid CSE technique due to concerns about associated risk factors such as fetal bradycardia. Fetal bradycardia is thought to occur from the rapid onset of spinal analgesia and reduction of beta adrenergic activity. The remaining alpha activity leads to uterine contraction and therefore decreased uteroplacental blood flow. The CSE technique can further delay confirmation of a functional epidural catheter. This delay could result in complications if instrumented or emergent delivery is imminent.

In a novel technique described by Cappiello *et.al*, a dural puncture epidural (DPE) is performed by creating a perforation in the dura with a spinal needle through an epidural needle without drug administration into the intrathecal space. The return of cerebral spinal fluid (CSF) through the spinal needle is thought to provide indirect confirmation of the correct position of the Tuohy needle. The EPL catheter is then tested and dosed in usual fashion with more immediate assessment of a functional EPL catheter. In theory, the DPE technique provides confirmation of midline placement of epidural catheter. Additionally, the dural perforation allows for translocation of medications administered in the epidural space into the spinal cavity. This has been shown to reduce time to achieve adequate pain relief from labor and reduce rates of uneven sensory block. As reported by Cappiello *et. al.*, catheter replacement

decreased from 13% to 3% when introducing DPE. Their group also reports that unilateral blocks decreased from 25% to 8% and catheter adjustments from 28% to 13%. The same group completed a subsequent study that has been accepted for publication, which reports that clinician-administered epidural interventions, or "top-ups" also decreased from 50% to 22.5% when introducing the DPE technique. The same group also reports that clinician administered epidural interventions, or "top-ups" also decreased from 50% to 22.5% when introducing the DPE technique.

There has been no prospective study to date to compare the standard epidural technique to the DPE technique for labor analgesia in the morbidly obese population.

Purpose of the study:

The primary purpose of this study is to determine if there are differences in block quality between the DPE and standard EPL techniques for labor analgesia in the morbidly obese patient. Establishing superiority of a technique is multifaceted and complex; therefore, the design of the study will define a set of measureable outcomes to assess these properties, which will be addressed in the subsequent sections. We hypothesize that when compared to the standard EPL, the DPE technique will significantly improve block quality in this population.

The secondary purpose of the study is to find an optimal maintenance regimen for epidural analgesia in the morbidly obese population. For the maintenance of epidural analgesia, it is common practice to use either continuous epidural infusion or a programmed intermittent bolus using a solution of ropivicaine 0.1% with fentanyl (2 mcg/mL). To date, there are no randomized prospective studies that investigate maintenance regimens in the morbidly obese parturient population. What has been shown is that super morbidly obese patients have increased intra-abdominal and intracranial pressure which increases pressure in the epidural space. Because of this elevated pressure, the epidural spread is increased, resulting in higher sensory blocks than necessary for adequate labor analgesia. ¹⁵ An important consequence is that the morbidly obese

parturient may experience additional undesirable side effects to a labor epidural: increased respiratory function, increased incidence of hypotension, and increased motor block.

Design and procedures:

We propose a prospective, double-blinded, randomized trial. According to our patient population and incidence of morbid obesity, enrollment would likely occur over a 2 to 3-year period. We have a delivery rate of 3500 per year. Previous data from our institution show that at least 11% of our patients are morbidly obese. We will therefore expect 800-900 morbidly obese women to deliver at our institution per year. We anticipate to complete enrollment before the protocol's third annual renewal.

Subject identification and recruitment:

Women admitted to the Duke Birthing Center for spontaneous or induced vaginal delivery will be screened. After usual consultation with the anesthesia team is completed and consent for anesthesia services are obtained, eligible patients will be approached to by a member of the study team. As indicated below, we will plan to enroll 130 patients (65 for the DPE group and 65 for the EPL group) and consent 150 women to reach this goal.

Inclusion criteria for study eligibility include: ages 18-45, singleton, vertex fetuses at 37-41 weeks' gestation, nulliparous and multiparous women, cervical dilation of 2-7cm, BMI ≥ 35 kg/m², pain score > 4, and English-speaking ability. Women with diseases of pregnancy that increase the risk of assisted vaginal delivery or cesarean delivery (i.e. major cardiac disease, chronic pain, chronic opioid use, prior cesarean delivery, and maternal pelvic/hip disease) are will be excluded from the study. Women who cannot speak English will be excluded. *Subject competency:* Only competent subjects will be approached to participate in this study. *Costs to the subject:*

There will be no additional cost to the subjects as a result of participation in this research study. There will be no compensation to patients for their participation in this study.

Epidural technique:

Once the patient requests a labor epidural, the usual standard of care for epidural placement will be initiated. The patient will have at least one 18g intravenous catheter and will receive 500-1000mL fluid administration. Vitals will be monitored by the labor nurse, including continuous pulse oximetry, non-invasive blood-pressure monitoring, and external tocodynamometry. Anesthesia time-out will be performed by the anesthesia provider with participation from the nurse and the patient.

All patients will receive a neuraxial technique in the sitting position at L3/4 or L4/5 using loss of resistance to saline. In the DPE group, a 25-g Whitacre needle will be used to puncture the dura. In both groups, the epidural catheter will be threaded 5 cm in the epidural space with an initiation dose of 15 ml of ropivacaine 0.1% with fentanyl (2 mcg/ml) over 6 minutes as per standard practice. Labor analgesia will be maintained by programmed intermittent bolus with 6 ml of the same solution every 45 minutes starting 30 minutes after the initial dose. Patients will have patient-controlled epidural analgesia (PCEA) available with an 8 ml dose per demand, every 10 minutes, for a maximum dose of 45 ml for every hour.

Assignment of Study Cohorts:

Study participants will be randomized by computer-generated sequence to EPL or DPE arms, stratified by class of obesity (BMI \geq 35<40 kg/m², \geq 40<50 kg/m² and \geq 50 kg/m²) and by parity (nulliparous versus multiparous). Patients will be assigned to one of the four study arms by computer-generated, randomized sequence in order to balance baseline characteristics across the arms. This will be a double-blinded study. After the consented and enrolled participant

requests labor epidural, a study member will give the anesthesia provider a sealed envelope with study assignment for either standard EPL or DPE technique.

Protocol for Breakthrough Pain

- If the patient has uneven or unilateral level, the provider will withdrawal catheter 1cm from skin and bolus 5ml of epidural mix. As fetal heart rate allows for maternal repositioning, the patient will lay lateral position with unblocked side in the dependent position. (up to 3 catheter adjustments)
- If the patient has bilateral levels at that below T10 to ice, the patient will be administered 5 ml off epidural pump, up to 3 times in 15 minutes.
- If the patient has pain despite T10 levels, the provider will administer Fentanyl 100 mcg via epidural.
- If analgesia continues despite these interventions up to 3 times within 60 minutes, the attending anesthesiologist will determine if epidural catheter needs replacement.

Data analysis and monitoring:

The primary outcome of this study is block quality which will be defined by a composite of five components (1) asymmetric block after 30 minutes of initiation, (2) top-up interventions, (3) catheter adjustments (4) failed catheter requiring replacement, and (5) failed epidural requiring general anesthesia or replacement neuraxial anesthesia for emergency cesarean section. The composite outcome is a practical endpoint for our study because while necessary to determine block quality, incidence of failed epidural or one-sided epidurals are rare. All five components are of similar importance when assessing the quality of epidural analgesia. Therefore, this outcome definition will increase the power of the study, without sacrificing clinical relevance or feasibility.

Block level will be measured by temperature discrimination with ice, and levels that are greater than two dermatomal levels would be considered asymmetric. Lower extremity dermatomal levels will be assessed by stimulating the inguinal crease (L1), anterior thigh (L2), medial knee (L3), medial malleolus (L4), between the great and second toe (L5), the lateral heel (S1), and the medial popliteal fossa (S2). On the thoracic levels, the torso will be assessed bilaterally at the mid-clavicular line.

Secondary outcomes include time to numeric pain rating scale ≤1, maternal adverse events (hypotension, fetal bradycardia, PDPH), motor block, duration of second stage of labor, total labor epidural time, total anesthetic dose required, PCEA use, and mode of delivery.

Statistical Methods:

The primary assessment of difference in the composite outcome between the two epidural techniques will be conducted via chi-square test. Using data from a recent retrospective study on labor maintenance regimens published by our group, we expect the composite event rate to be 35% in the group receiving EPL.¹⁷ Based on the findings by Hess *et al.* of a 62% relative reduction in breakthrough pain with a CSE technique compared to an EPL, we will define a clinically meaningful effect in our study as a similar reduction in the composite outcome to be 14% in the DPE group, which corresponds to an odds ratio of $0.30.^{18}$ A two-sided χ^2 test for the difference in composite outcome rates between epidural techniques at alpha level 0.05 will reach 80% power to detect an odds ratio of 0.30 comparing DPE to EPL in a study of 130 patients (65 DPE and 65 EPL).

Further analysis of the difference in the composite outcome between the two epidural techniques will be conducted via multivariate logistic regression to account for potential confounders. Comparison of additional secondary outcomes between the epidural techniques of

maternal adverse events, total labor epidural time, total anesthetic dose required, mode of delivery, and degree of motor block will be compared with χ^2 tests and logistic regression. The time to numeric pain rating scale ≤ 1 will be compared between the two epidural techniques via Kaplan-Meier estimates and log-rank tests.

Data will be monitored closely for the occurrence of adverse events (AE) and reported to the IRB as needed. If unanticipated AEs or if expected events appear to be occurring more frequently than expected, those AEs will be explored per treatment arm.

In accordance with federal regulations, the PI will monitor for, review, and promptly report to the IRB, appropriate institutional officials, sponsor, coordinating center and the appropriate regulatory agency head all unanticipated problems involving risks to subjects or others that occur in the course of a subject's participation in a research study (45 CFR 46.103(b)(5)(i) and 21 CFR 56.108(b)(1)), all AE reports will be reported per the DUHS IRB policies.

Data storage and confidentiality:

Study records will remain confidential as required by law. Federal Privacy regulations ensure privacy, security and authorized access. Patient identifiers including but not limited to name, social security number, address, and telephone number will not be disclosed outside of the Duke University Health System (DUHS). For records shared with parties outside of DUHS, patients will receive a unique code number. The key to the code will be kept in a locked file in [name] office.

Risk/benefit assessment:

The will be no benefit to subjects from participating in the study, since standard of care regimens will be used in this study. The information gained from the study will help elucidate if

DPE offers benefits over standard EPL for initiation and maintenance of labor analysis in our practice. Risks of epidural analysis are the same irrespective of participation in the study. These are 1.5% rate of unintentional dural puncture with epidural needle, <1% risk of post-dural pucture headache, inadequate analysis, and unintentional intravascular or subarachnoid injection. ^{19,20}

References:

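### The aim of identifying the best maintenance regimen has no regimen comparison behind it, and one sentence gives four arms where the rest of the plan has two

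*Combined protocol and SAP*

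**What the plan says.** Purpose of the study gives two purposes. The primary one is block quality, DPE against EPL. The other reads: "The secondary purpose of the study is to find an optimal maintenance regimen for epidural analgesia in the morbidly obese population". The same paragraph says that "it is common practice to use either continuous epidural infusion or a programmed intermittent bolus" and gives the evidence gap as the reason: "To date, there are no randomized prospective studies that investigate maintenance regimens in the morbidly obese parturient population".

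Epidural technique then describes one regimen: "Labor analgesia will be maintained by programmed intermittent bolus with 6 ml of the same solution every 45 minutes", with one PCEA setting on top. Initiation is also common to all patients: "In both groups, the epidural catheter will be threaded 5 cm in the epidural space with an initiation dose of 15 ml".

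Assignment of Study Cohorts randomizes to EPL or DPE, stratified by three BMI classes and two parity groups, and the sealed envelope carries the technique only. Between these two statements, one sentence refers to four arms without defining them. Subject identification and recruitment and Statistical Methods both give 65 patients per technique.

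The planned analyses are:
- "The primary assessment of difference in the composite outcome between the two epidural techniques will be conducted via chi-square test";
- "Further analysis of the difference in the composite outcome between the two epidural techniques will be conducted via multivariate logistic regression";
- for the remaining listed outcomes, "Comparison of additional secondary outcomes between the epidural techniques", by chi-square and logistic regression;
- for time to a low pain score, Kaplan-Meier and log-rank, again by technique.

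Risk/benefit assessment says the study should show whether DPE is better than EPL both in starting and in maintaining analgesia.

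**The concern.** Choosing the best of several regimens needs at least two regimens and a comparison between them. The plan has one regimen and none of the comparisons. This is a matter of design, so more patients or a different model would not help. A report that follows the protocol must either drop a declared purpose without comment or make a statement about regimens that has no randomized support.

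The four-arm sentence matters because it governs allocation. If it is a slip, it is clerical. If the randomization list really has four arms, a second factor exists that the protocol neither describes nor analyzes.

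A related gap affects the outcomes that could speak to maintenance. Total anesthetic dose is assigned chi-square and logistic regression although it is a quantity and no categories are given. PCEA use is listed as an outcome but has no test.

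**Working it through.** **1. Aim against design**

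| Item | Section | Content |
|---|---|---|
| Regimens named as options | Purpose of the study | 2 |
| Regimens given | Epidural technique | 1 |
| Factor randomized | Assignment of Study Cohorts | technique |
| Content of envelope | Assignment of Study Cohorts | technique |
| Planned comparisons by technique | Statistical Methods | 4 of 4 |
| Planned comparisons by regimen | Statistical Methods | 0 of 4 |

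The total of four treats the chi-square tests and logistic regressions on the other secondary outcomes as one item. Counted another way the total changes, but the number by regimen stays at zero. The only other contrast is a look at adverse events by treatment arm, which names no regimen.

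**2. Arm count**

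Strata: 3 BMI classes × 2 parity groups = 6, so four is not a miscounted number of strata. Sample size: 65 + 65 = 130 fits two arms. An equal split over four gives 130/4 = 32.5, which is not a whole number, although unequal arms would be possible.

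**3. The plan's own sample size, for two arms**

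Inputs from Statistical Methods: event rates 0.35 (EPL) and 0.14 (DPE), two-sided alpha 0.05, n = 65 per arm.

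- Odds ratio: (0.14/0.86)/(0.35/0.65) = 0.302, against the stated 0.30.
- Pooled rate: (0.35 + 0.14)/2 = 0.245. Difference: 0.21.
- z for power = [0.21·√65 − 1.96·√(2·0.245·0.755)] / √(0.35·0.65 + 0.14·0.86) = (1.693 − 1.192)/0.590 = 0.849.
- Power = Φ(0.849) = 80.2%. Exact enumeration of the uncorrected chi-square test gives 81.3%.

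The stated figures reproduce, and they are two-arm figures.

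**4. If the list had four arms**

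With 32 or 33 patients per arm, the same formula for one single arm against another at 35% and 14% gives 49.7% or 51.0% power. In a technique-by-regimen layout, technique could still be compared at about 65 against 65 by pooling over the second factor, but that would need its own justification. The documents describe no such layout, so this shows only why the list should be checked.

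**5. Dose as a description of maintenance**

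The programmed schedule alone delivers 6 × 60/45 = 8 ml per hour. Total dose therefore rises with time on the epidural, before any patient or clinician bolus, and it includes the common 15 ml initiation dose. Total labor epidural time is already a planned outcome, so a rate per hour can be formed from data the trial intends to collect.

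**The case against.** The strongest reply is that little depends on the regimen aim. The hypothesis, the listed outcomes and the analyses are all about technique, so the plan as written would not produce a claim about the best regimen, and no planned result is wrong. That stands, and it limits the severity. It does not make the aim answerable.

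A second reply is that maintenance is covered: Risk/benefit assessment frames the question as DPE against EPL in starting and maintaining analgesia, and dose, PCEA use and motor block can address it. This also stands, and it favors restating the aim over deleting it. But those outcomes describe use under one regimen, by technique; they cannot rank regimens. The same section refers to standard-of-care regimens in the plural, but it names no second maintenance regimen.

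A reader might infer that the trial is really a technique-by-regimen design with four arms, and that the second factor was left out. That would explain both the regimen aim and the arm count. The documents do not say so: randomization text, envelope, sample size and analyses all have two groups. Equally, they do not show that the two defects are unrelated.

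**Conclusion.** The concern holds in a limited form. One of the two stated purposes cannot be met, because one regimen is described and none of the planned comparisons is between regimens. The arm count is inconsistent within Assignment of Study Cohorts and must be reconciled. Severity is minor to should-fix.

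A reader might go further and infer that the primary comparison is invalid or underpowered. The documents do not support that: 130 patients and 80% power reproduce for the two-arm test of 35% against 14%. That reassurance rests on one assumption, that the randomization list has two arms within the six strata. The list is not in the documents, so the effect on the primary analysis is nil only once this is confirmed.

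The point about tests is smaller but independent. Whether or not the aim is kept, total dose needs a test suited to a quantity, and PCEA use needs a named test.

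**What to change.** 1. Reconcile Purpose of the study with Epidural technique, Assignment of Study Cohorts and Statistical Methods. Either withdraw the regimen aim, or restate it as DPE against EPL during maintenance under the single regimen, using anesthetic dose, PCEA use and motor block. The second route matches Risk/benefit assessment. No change of regimen is proposed.
2. In either case, name a two-group test for quantities, such as the rank-sum test, for total anesthetic dose and PCEA use. If dose is used to describe maintenance, express it per hour of epidural time and state whether the initiation dose is included.
3. Check the randomization list. If it has two arms, correct the arm count to two. If it has four, describe the second factor and reconsider the analysis and sample size before any comparison is made.

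The cost is a wording amendment, two named tests and one check of the list. With two arms confirmed, no extra patients are needed. The downside is a narrower stated scope: the trial gives up a claim about regimens that it could not have supported.

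### Does the stated yearly pool of 800-900 morbidly obese women, which does not follow from 3500 deliveries and an 11% floor, call for a change to the plan?

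*Combined protocol and SAP*

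**What the plan says.** The opening paragraph of Design and procedures in the combined protocol and SAP makes the recruitment case in this order:

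- Duration: "According to our patient population and incidence of morbid obesity, enrollment would likely occur over a 2 to 3-year period".
- Volume: "We have a delivery rate of 3500 per year".
- Prevalence, as a lower bound from the institution's earlier data: "at least 11% of our patients are morbidly obese".
- Resulting pool: "We will therefore expect 800-900 morbidly obese women to deliver at our institution per year".
- Completion: "We anticipate to complete enrollment before the protocol's third annual renewal".

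Subject identification and recruitment then sets a target of 130 enrolled (65 per technique) and plans to "consent 150 women to reach this goal". Entry requires, among other criteria, "BMI ≥ 35 kg/m², pain score > 4, and English-speaking ability". Under Assignment of Study Cohorts, randomization is "stratified by class of obesity", with the lowest stratum running from BMI 35 to below 40. No BMI cut-off is attached to the 11%, and no other prevalence or delivery count appears in the document.

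**The concern.** The pool is presented as a consequence of the two figures just before it, and it is not one. Multiplying them gives less than half of what is stated. The mismatch sits in the paragraph that justifies the enrolment period, and 800-900 is the only yearly count of potential participants offered.

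If the inputs are right and the result is wrong, the share of morbidly obese women who must consent is at least about double what the text suggests, before any loss to the gestational-age, dilation, pain-score, language and prior-cesarean criteria. A reader could fear that the timetable was built on an inflated pool, that accrual will be slow, and that the trial could end short of 130 with less power than planned. The missing BMI cut-off adds to the doubt, because the pool at the entry threshold is not explicitly given.

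**Working it through.** **Inputs.** From Design and procedures: 3500 deliveries a year; prevalence 11% or more; stated pool 800-900 a year; enrolment over 2 to 3 years. From Subject identification and recruitment: 150 consents for 130 enrolled. From Statistical Methods: composite event rates of 35% and 14%, two-sided alpha 0.05, 65 per arm.

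**1. Attempt to reproduce the stated pool.** Pool = deliveries x prevalence = 3500 x 0.11 = 385 a year. Rounding does not close the gap: 3500 x 0.105 = 367.5 and 3500 x 0.115 = 402.5. The ratios are 800/385 = 2.08 and 900/385 = 2.34. The stated figure is not reproduced.

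**2. What would make 800-900 correct.**

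- A higher prevalence at 3500 deliveries: 800/3500 = 22.9% to 900/3500 = 25.7%. This is compatible with a floor of 11%, but is stated nowhere.
- More deliveries at 11%: 800/0.11 = 7273 to 900/0.11 = 8182 a year, which conflicts with 3500.
- A total over several years: 800/385 = 2.1 to 900/385 = 2.3 years. This lies within the planned enrolment period and would make the words for a single year the slip.

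The document does not decide between these.

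**3. Effect on the timetable.** Share of the pool that must consent = 150 / (yearly pool x years).

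| Yearly pool | Basis | Pool over 2 years | Share | Pool over 3 years | Share |
|---|---|---|---|---|---|
| 385 | 11% floor | 770 | 19.5% | 1155 | 13.0% |
| 525 | 15%, assumed | 1050 | 14.3% | 1575 | 9.5% |
| 700 | 20%, assumed | 1400 | 10.7% | 2100 | 7.1% |
| 800 | stated, low end | 1600 | 9.4% | 2400 | 6.3% |
| 900 | stated, high end | 1800 | 8.3% | 2700 | 5.6% |

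Per month, 150/36 = 4.2 to 150/24 = 6.3 consents are needed. They would come from 385/12 = 32 such deliveries at the floor, against 800/12 = 67 to 900/12 = 75 on the stated pool.

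These shares are not consent rates, because many women in the denominator will be ineligible or will not request an epidural. If a fraction e of the pool can be approached, the required consent rate is the share divided by e. At the floor, the target is arithmetically out of reach only if e falls below 19.5% (two years) or 13.0% (three years). The document gives no e, so neither comfort nor failure can be shown from it.

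**4. Effect on sample size and power.** The normal approximation with pooled variance under the null uses a difference of 0.35 - 0.14 = 0.21 and a mean rate of 0.245.

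- Null standard error: sqrt(2 x 0.245 x 0.755 / 65) = 0.0754.
- Alternative standard error: sqrt((0.35 x 0.65 + 0.14 x 0.86) / 65) = 0.0732.
- Power = Phi((0.21 - 1.96 x 0.0754) / 0.0732) = 0.802.

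This agrees with the stated 80%. Neither the delivery count nor the prevalence enters it.

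**The case for a change.** The strongest case for a correction is that the figure has a job. The enrolment period is said to rest on the patient population and how common morbid obesity is, and 800-900 is the only yearly pool derived beside it. On the protocol's own inputs, that support is overstated by a factor of two or more. Even an assumed prevalence of 20% gives only 700 a year. Each way of rescuing the number, whether a wider BMI group or a mislabelled multi-year total, still leaves the sentence wrong or unclear as written. Reconciling three figures would also cost almost nothing.

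The arithmetic in that case stands in full, and nothing elsewhere in the document closes the gap. The consequence does not follow:

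- The enrolment period is stated before the pool, and no eligibility rate, consent rate or monthly accrual is worked out from 800-900. The text does not show that the timetable was calculated from it. If the figure is really a total over about 2.1-2.3 years, the timetable already reflects the smaller pool.
- Slow accrual would lengthen the trial. The target of 130 is fixed, and no rule ends recruitment on a calendar date; the third annual renewal is only an expectation.
- Replacing 800-900 with 385 could itself introduce an error. The 11% is a floor, and if it was counted at a stricter BMI cut-off than the entry threshold of 35, then 385 understates the relevant pool. A plain reading is that the protocol uses morbidly obese for its whole population from BMI 35 upward, but it does not say so.

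**Conclusion.** This is a clerical slip in the feasibility text, and no change to the plan follows. The stated pool is 2.08 to 2.34 times what its inputs give, and the document does not show which of the three figures is at fault. Design, allocation, sample size, power (0.802 at 65 per arm) and analysis are the same whichever figure is right, so a trial run as written recruits to the same target and supports the same conclusions.

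The most that can be said against the timetable is that its margin is thinner than the text suggests. At the 11% floor, 13.0-19.5% of the pool must consent over three or two years, rather than 5.6-9.4%. That does not show two to three years to be unachievable.

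The conclusion rests on two readings of the document: that 11% is a lower bound, as stated, and that 800-900 is used nowhere beyond the recruitment paragraph. It would need revisiting only if recruitment were to be closed on a fixed date regardless of the number enrolled, which the plan does not provide for.

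### Does calling the trial double-blinded, without naming who is masked, leave the primary composite open to unmasked judgment?

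*Combined protocol and SAP*

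**What the plan says.** The label appears twice. Design and procedures opens with "We propose a prospective, double-blinded, randomized trial", and Assignment of Study Cohorts repeats it: "This will be a double-blinded study". Neither place says which roles are masked or how.

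One person certainly learns the arm. After the patient asks for an epidural, "a study member will give the anesthesia provider a sealed envelope with study assignment for either standard EPL or DPE technique". Under Epidural technique, only the DPE arm has the spinal-needle puncture of the dura.

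The composite is defined under Data analysis and monitoring, and most of the actions behind it are described under Protocol for Breakthrough Pain:

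- **Asymmetric block at 30 minutes.** The ice method, test sites and two-dermatome threshold are given; the assessor is not named.
- **Top-ups.** For bilateral levels below T10, "the patient will be administered 5 ml off epidural pump, up to 3 times in 15 minutes", with no actor named. For pain despite adequate levels, "If the patient has pain despite T10 levels, the provider will administer Fentanyl 100 mcg via epidural"; whether this counts as a top-up is not stated.
- **Catheter adjustment.** "If the patient has uneven or unilateral level, the provider will withdrawal catheter 1cm from skin and bolus 5ml of epidural mix".
- **Catheter replacement.** After repeated interventions, "the attending anesthesiologist will determine if epidural catheter needs replacement".
- **Failure at emergency cesarean.** No decision-maker is named.

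**The concern.** A sealed envelope conceals the allocation until it is opened; it masks nobody afterwards. The protocol uses the word provider both for the person who opens the envelope and for the person who acts on breakthrough pain, and does not say that they differ. Read literally, one person who knows the arm could place the block, read the ice test and then decide on the adjustments and fentanyl dose.

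Top-ups, adjustments and replacements are clinician actions, and the hypothesis under Purpose of the study favors DPE. If knowledge of the arm altered the threshold for acting or recording, the composite rates would differ for a reason other than the technique. No record of whether each decision-maker knew the arm is described, so the effect could not be examined later. The time-out is a further possible route: "Anesthesia time-out will be performed by the anesthesia provider with participation from the nurse and the patient", with no word on whether the arm is mentioned.

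**Working it through.** **1. The plan's own figure.** Inputs from Statistical Methods: 35% (EPL), 14% (DPE), two-sided alpha 0.05, chi-square test, 80% power, 65 per arm.

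n per arm = [z(0.975)·√(2p̄(1−p̄)) + z(0.80)·√(p1(1−p1) + p2(1−p2))]² / (p1−p2)²

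With p̄ = (0.35 + 0.14)/2 = 0.245:

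- √(2 × 0.245 × 0.755) = 0.6082
- √(0.35 × 0.65 + 0.14 × 0.86) = 0.5898
- n = (1.960 × 0.6082 + 0.8416 × 0.5898)² / 0.21² = 64.7, rounded up to 65 per arm, 130 in all

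Power at 65 per arm is 80.2% by this formula. Enumerating all pairs of binomial counts with the uncorrected Pearson test gives 81.3%. The stated design reproduces, and masking does not enter it.

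**2. What a shift would do.** The documents give no figure for bias from knowing the arm, so every shift below is an assumption. The method is the same exact enumeration (65 per arm, uncorrected chi-square). The shift is split equally between arms: around 35% for type I error, and against the planned difference for power.

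| Assumed shift between arms | Patients (shift × 65) | Rates, no true effect | Type I error | Rates, planned effect shrunk | Power |
|---|---|---|---|---|---|
| 0 points | 0 | 35 / 35 | 5.3% | 35 / 14 | 81.3% |
| 0.9 points | 0.6 | 35.45 / 34.55 | 5.4% | 34.55 / 14.45 | 77.7% |
| 5 points | 3.25 | 37.5 / 32.5 | 9.6% | 32.5 / 16.5 | 57.5% |
| 10 points | 6.5 | 40 / 30 | 23.1% | 30 / 19 | 31.3% |

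A 5-point shift is 5/21 = 24% of the planned difference. The results run from negligible to material according to the shift chosen, so they do not show that a problem exists. They also apply to the composite as a whole. A misjudged component changes a patient's status only if she has no other component, so a given rate of misjudged components moves the composite by that amount at most, and usually by less.

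**3. What the text establishes for each role.**

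- *Operator:* knows the arm. This is unavoidable, because the operator performs or omits the dural puncture.
- *Patient:* not said to receive the assignment. Both arms share the sitting position, the interspace options, catheter depth, initiation dose and maintenance regimen; the documented difference is the needle pass.
- *Ice-test assessor:* unnamed and not said to be the operator. Method, sites and threshold are fixed in writing.
- *Breakthrough-pain clinicians:* not said to be the operator and not said to be masked. Their steps fall under a heading about pain, so the pathway appears to start with the patient's complaint, and the adjustment and top-up steps have written triggers.
- *Time-out:* the protocol says neither what is disclosed nor whether it comes before or after the envelope is opened. Silence about a routine safety check is not evidence of a leak.

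The text therefore shows one unmasked role, which has to be so. For the others it is silent, under a general statement that the trial is double-blinded.

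**The case for a change.** The best case for a change is that the label cannot be checked. Double-blinded has no content until the roles are named, and the only sentence on who learns the arm names a clinician. Replacement is expressly left to the attending's judgment, and failure at cesarean has no written trigger. Fixed ice-test criteria and written triggers limit judgment without removing it. Stating the roles, and having a study member who was absent from placement do the ice test, looks cheap.

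Much of this stands as description: the roles are not named, and some judgment remains. It does not carry through to a change, for three reasons.

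- It argues from silence. Using an assessor who knows the arm would go against the trial's own label, so a team following the protocol would not do so.
- The remedy adds little. It would newly mask only the ice test, which the label already implies. The clinician-driven components would stay with the same people, with at most a descriptive data field added. Relabelling the trial if any role cannot be masked would always be triggered, because the operator never can be.
- The low cost is itself assumed. The protocol says only that a study member hands over an envelope, not whether that person sees the assignment or is free 30 minutes later.

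**Conclusion.** No change to the plan is needed. The omission is real: the protocol does not say who is masked, how, or who reads the 30-minute test. It is missing detail that a trial team fills sensibly, with the operator unmasked by necessity and the patient and the assessor unaware of the arm. Unmasked determination of primary components is possible on the text but not shown by it.

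The size is unknown. If one line of scale is wanted, an assumed 5-point shift between arms (about 3 of 65 patients) around 35% raises the exact type I error from 5.3% to 9.6%; the 5 points are not drawn from the documents. Neither the sample size of 130 nor the chi-square test is affected.

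The conclusion rests on two readings: that the double-blinded statement governs whoever assesses outcomes, and that the provider acting on breakthrough pain need not be the one who placed the block. A statement that the operator also performs the ice test would overturn it; the protocol contains none.
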